Statistical Considerations	
Descriptive statistics (response rate, time to response, progression-free survival). Comparison to historical controls of nirogacestat alone and Stanford-treated cryoablation patients.
 
The primary outcome is clinical benefit rate (CR + PR + SD) at 1 year. We plan to enroll a total of 20 subjects. Assuming a null CBR of ≤ 0.5 versus an alternate CBR of 0.8, we have a maximum statistical power of 100.0% to detect a difference of 0.3 using a one-sided exact test with a type 1 error of 0.05.

Study Duration	
Duration of treatment for a subject via this study protocol is up to 24 months (26 cycles of treatment). This study will be complete when the last study data, including follow-up, has been collected, and analysis is complete. The duration of enrollment for this study will be approximately 25 months (including the initial 28-day screening period). Based on the determination of clinical benefit after 12 months' treatment, and 3 months for analysis of the primary endpoint, preliminary results for the primary endpoint are expected to be available approximately 40 months from the start of enrollment. Based on 25 months to completely enroll, and overall individual treatment period of approximately 24 months, the overall period until treatment is complete will be about 49 months from the start of enrollment. The complete final analysis (including primary and secondary analyses and safety assessments) and termination of all study activities is expected to be at about 53 months.
 
Key milestones are as follows.
 
• The per-subject screening period is approximately 28 days.• The duration of enrollment (minus the screening period) is approximately 24 months.• The per-subject primary endpoint (clinical benefit) is assessed after 12 months' treatment.• The per-subject duration of treatment is approximately 24 months (26 cycles of treatment).• Final subject visit is about 30 days after last treatment.• Nominal duration of subject participation is up to about 26 months.• Final study analysis is expected to take about 3 months.
Subject Duration	Approximately 26 months (28-day screening period, approximately 24 months of treatment, and End of Treatment visit about 30 days after last study treatment).

PROTOCOL SCHEMA

Subject Consent

Screening (Day 1 to Day 28):

(Collect archival histology report, EQ-5D-3L questionnaire, ECG, serum pregnancy test, routine labs & scans).

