1.2. Background

1.2.1. Study Disease

Desmoid tumor is a non-metastasizing but locally aggressive neoplasm that can occur anywhere throughout the body. Desmoids are rare with an estimated incidence in the general population of 2 to 4 per million population per year.² Affected populations can occur in any age group, most commonly seen between the ages of 15 to 60, with a slight preponderance among women than men. Affected locations can include upper and lower extremities, trunk, head and neck region, abdominal wall, and intra-abdominal. The natural history of desmoid is extremely

variable and there are some tumors that spontaneously regress, some that remain stable for years, and some that have unrelenting growth. Tumors that occur intra-abdominally and are associated with familial adenomatous polyposis (FAP) tend to be multi-focal, more aggressive, and potentially fatal. Under histologic exam, desmoid tumors appear as spindle cells in an abundant fibrous stroma with low cellularity, few mitotic figures, and absent necrosis. Staining for nuclear beta-catenin is commonly seen and a fair amount of desmoids have mutations in Catenin Beta 1 (CTNNB1). Other mutations seen are adenomatous polyposis coli (APC) mutations, which are found in FAP patients.

For growing desmoid tumors, options include surgical resection (which can be morbid and has a high recurrence rate), radiation therapy, systemic therapy [such as chemotherapy or vascular endothelial growth factor receptor tyrosine kinase inhibitors (VEGF-TKIs)], and more recently, ablation procedures, such as cryoablation or high intensity focused ultrasound (HIFU).

However, each approach has its pros and cons. For radiation therapy, local control rates are excellent, with approximately 80% at 3 years, however, there are potentially devastating albeit rare long-term side effects such as secondary malignancies.³ For systemic therapy, the time to response is longer (sorafenib trial median of 9 months), and there is associated systemic toxicity. Chemotherapy (doxil, methotrexate/vinblastine) have higher response rates and faster time to response; however, they have more significant side effects than TKIs. For ablation procedures, it may not be technically feasible to totally treat the tumor due to proximity to critical structures such as nerve and skin, there is often a need for multiple treatment sessions. Tumor recurrence or progression is inevitable for tumors that cannot be completely ablated.

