An investigator-initiated phase 2, open-label, single-center study was sponsored and conducted by the National Cancer Institute (NCI) to evaluate the objective response rate (ORR) after therapy with nirogacestat in subjects with recurrent, refractory, progressive desmoid tumors (Kummar et al., 2017). 17 subjects received daily doses of nirogacestat at the RP2D of 150 mg BID continuously in 3-week cycles. Response to treatment was evaluated at Cycle 1 and every 6 cycles (18 weeks) thereafter by RECIST v1.1. Of the 17 subjects treated in the study, 15 had mutations in APC or CTNNB1 genes. 16 subjects were evaluable for response with 5 (29%) subjects achieving PR after a median of 32 cycles (96 weeks) of nirogacestat. The remaining 11 subjects had a best response of stable disease (SD) and no instances of progressive disease were observed. All but 1 evaluated subject had a measurable regression of tumor volume by MRI. The AE profile was consistent with previous reports (Messersmith, et al., 2015; Kummar et al., 2017) and consisted of all subjects experiencing at least one TEAE with the majority being Grade 1 to 3. The most frequently ($\geq 70\%$) reported TEAEs were diarrhea (88%), headache (76%), hypophosphatemia (76%), AST increased (71%), lymphocyte count decreased (71%), and nausea (71%). A total of 10 (59%) subjects reported Grade 3 treatment-related TEAEs. Eight (47%) subjects reported Grade 3 hypophosphatemia, 1 (6%) subject reported Grade 3 diarrhea, 1 (6%) subject reported Grade 3 fatigue, and 1 subject (6%) reported Grade 3 menstruation irregular. Per the sponsor, the subject that reported the Grade 3 menstruation irregular TEAE was postmenopausal prior to enrolling in the study, and thus this event should not have been reported as a TEAE. A total of 9 (53%) subjects reported at least one SAE including 4 (24%) subjects reporting events considered by the investigator to be related to nirogacestat. No SAE was reported in more than one subject. The 4 SAEs that were considered by the investigator to be related to nirogacestat were blood bilirubin increased, hypersensitivity, squamous cell carcinoma, and vulvovaginal inflammation, which were each reported in a single subject. All related SAEs were reported as Grade 2 severity. A single event of Grade 2 hypersensitivity, considered by the investigator to be possibly related to study treatment, led to the permanent discontinuation of study treatment in one subject. There was one death on study due to a cerebrovascular accident that was assessed by the investigator to be unlikely related to nirogacestat. There were no TEAEs that were considered to be DLTs.

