
Study NIR-DT-301 was a multi-center, randomized, double-blind, placebo-controlled, parallel arm, Phase 3 study to evaluate the efficacy, safety, and tolerability of nirogacestat in adult patients with progressing DT/aggressive fibromatosis (AF). A total of 142 patients were randomized to study treatment (nirogacestat or placebo) in a 1:1 ratio to receive 150 mg BID of study treatment, continuously in 28-day cycles, or matching placebo. This study consisted of 2

phases: the double-blind phase and the optional open-label extension (OLE) phase, which is still ongoing.

A statistically and clinically significant improvement in the primary endpoint of PFS was observed for nirogacestat over placebo, with a 71% reduction in the risk of disease progression (HR = 0.29 (95% CI: 0.15, 0.55); p <0.001). The probability of being event free at 6-, 12-, and 24 months is consistently higher for nirogacestat as compared to placebo, supporting a sustained clinical benefit over time. Treatment with nirogacestat demonstrated a statistically significant improvement over placebo in ORR (41% vs 8%; P <0.001) with 5 patients reporting a CR in the nirogacestat arm as compared to 0 patients receiving placebo. Clinically meaningful and statistically significant improvements were also observed with all patient-reported outcomes (PROs) included in the testing hierarchy among patients receiving nirogacestat as compared to placebo with significant improvements noted early (beginning at the first post-treatment assessment in Cycle 2) and generally sustained throughout the course of the study (Mease et al. 2011; Osoba et al. 1998). Overall, results from the PRO analyses demonstrate improved quality of life with nirogacestat as compared to placebo.

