3.1.1. Inclusion Criteria

Prospective Participant Must Meet ALL these Inclusion Criteria to be Eligible	Yes	No	Supporting Documentation *

1. Histologically-confirmed diagnosis of desmoid tumor (DT) that is progressing (by RECIST criteria over the past 12 months) or symptomatic (as defined by change in pain regimen or impairment of activities of daily living (ADLs), or at investigator discretion).
 
Note: Must have diagnosis of desmoid tumor on pathology report.
			
Pathology Date: _____
 
Progress notes: _____

Prospective Participant Must Meet ALL these Inclusion Criteria to be Eligible	Yes	No	Supporting Documentation *

2. Desmoid tumor is 50 to <75% cryoablatable.
 
Tumors that are 50 to <75% (volume) ablatable in a single session which may be characterized by:
 
 a. Proximity (< 1 cm) to critical structures, such as nerves, vessels, bowel, or skin, at risk of injury during ablation, despite hydrodissection, and/or b. Large size (> 100 mL), and/or c. Complex shape, such that parts of the tumor cannot be reached from a single approach or subject position, and/or d. Thin, infiltrative components, where ablation of that portion would damage more normal anatomy than tumor (e.g., tumor extending along a fascial plane between muscles, such that ablation would damage more muscle than tumor volume) 			

3. If participant is currently being treated with any therapy for the treatment of DT, this must be completed at least 28 days (or 5 half-lives, whichever is shorter) prior to first dose of study treatment. All toxicities from prior therapy must be resolved to ≤ Grade 1 or clinical baseline.
			

4. Participants who are receiving chronic nonsteroidal anti-inflammatory drugs (NSAIDs) as treatment for conditions other than DT must be on a stable dose for at least 28 days prior to first dose of study treatment.
			

5. Age ≥ 18 years.
			

6. Participant has an Eastern Cooperative Oncology Group (ECOG) performance status ≤ 2 at screening.
			ECOG: _____ Date of ECOG: _____

Prospective Participant Must Meet ALL these Inclusion Criteria to be Eligible	Yes	No	Supporting Documentation *

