10.2. Study Endpoints and Analyses

10.2.1. Primary Endpoint and Analysis

10.2.1.1. Primary Endpoint

The clinical benefit rate (CBR) is defined as the number and proportion of participants who are assessed with either a complete response (CR), a partial response (PR), or stable disease (SD) prior to 1 year after treatment start and show no evidence of loss of response nor progression

within that year. Response and progression will be assessed according to the Revised Response Evaluation Criteria in Solid Tumors (RECIST) v1.1.

10.2.1.2. **Primary Analysis Plan**

The primary analysis will be the calculation of the clinical benefit rate, (CBR), defined as the percentage of subjects in the analysis population who achieve a complete response (CR), partial response (PR), or stable disease (SD) as measured at 12 months \pm 1 month (approximately 1 year) from the start of treatment. CR, PR, and SD are as defined by RECIST v1.1. (See Appendix C RECIST v1.1). The CBR and the two-sided 95% Clopper-Pearson (exact) confidence interval will be calculated.

The analysis population will include all subjects who started nirogacestat and underwent cryoablation. Subjects who withdraw from the study prior to start of treatment or before receiving cryoablation and completing 1 year of treatment will be replaced.

10.2.1.3. **Relevant Subset for Primary Objective and Endpoint**

Evaluable subjects are those subjects who have received cryoablation therapy and completed 1 year of treatment.

10.2.1.4. **Primary Objective and Endpoint Assessment Methods**

CBR will be evaluated on the basis of clinical response as measured using imaging by MRI scan and evaluated by RECIST v1.1 (Appendix C). Determination of response will be made by the treating investigator.

10.2.1.5. **Measurement Time Points for Primary Objective / Outcome**

Imaging will be performed at screening, then every 3 cycles (ie, every 12 weeks \pm 14 days) until End of Treatment. MRI scan will be used at screening and at subsequent time points.

10.2.2. **Secondary Endpoints and Analysis**

10.2.2.1. **Clinical Benefit Rate (CBR) assessed by modified RECIST**

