10.4.4. Criteria for Future Studies

With our total sample size of 20, we will reject the null hypothesis and conclude that the treatment is efficacious if the number of responses is ≥ 11 . Otherwise, we will conclude that that the treatment is not promising.

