2.3.1. Evaluation of target lesions

Complete Response (CR): Disappearance of all target lesions. Any pathological lymph nodes (whether target or non-target) must have reduction in short axis to < 10 mm.

Partial Response (PR): At least a 30% decrease in the sum of diameters of target lesions, taking as reference the baseline sum diameters.

Progressive Disease (PD): At least a 20% increase in the sum of diameters of target lesions, taking as reference the smallest sum on study (this includes the baseline sum if that is the smallest on study). In addition to the relative increase of 20%, the sum must also demonstrate an absolute increase of at least 5 mm. (Note: the appearance of one or more new lesions is also considered progression).

Stable Disease (SD): Neither sufficient shrinkage to qualify for PR nor sufficient increase to qualify for PD, taking as reference the smallest sum diameters while on study.

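### The pooled clinical benefit rate mixes RECIST-progressing tumors with symptomatic-only tumors that need not be growing, stable disease counts as success for both, and the entry mix behind the 50% null is not stated

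*Protocol*

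**What the plan says.** **Entry.** Criterion 1 in section 3.1.1 (repeated in 2.1.3) accepts RECIST progression over the past 12 months, or a tumor that is "symptomatic (as defined by change in pain regimen or impairment of activities of daily living (ADLs), or at investigator discretion". The alternatives are joined by "or" and share one Yes/No box on the eligibility checklist.

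**Endpoint.** Section 10.2.1.2 counts subjects "who achieve a complete response (CR), partial response (PR), or stable disease (SD) as measured at 12 months", give or take a month. Appendix C defines stable disease as "Neither sufficient shrinkage to qualify for PR nor sufficient increase to qualify for PD", so a tumor that does not change is a success.

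**Decision.** Section 10.4.2 tests a single null of 0.5 against 0.8 at one-sided 0.05 with 20 subjects. Section 10.4.4 states that "we will reject the null hypothesis and conclude that the treatment is efficacious if the number of responses is" at least 11. The count is pooled over entry routes.

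**Basis of the null.** Section 10.4.3 takes 0.5 from local experience of more than 50% recurrence at 1 year after subtotal cryoablation. It does not say whether those tumors were growing, symptomatic or both when treated.

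**Natural history.** Section 1.2.1 describes "some tumors that spontaneously regress, some that remain stable for years, and some that have unrelenting growth".

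**Comparators.** The synopsis plans a "Comparison to historical controls of nirogacestat alone and Stanford-treated cryoablation patients". Section 1.2.4 describes the NCI phase 2 study as testing "nirogacestat in subjects with recurrent, refractory, progressive desmoid tumors" and the phase 3 study NIR-DT-301 as enrolling "adult patients with progressing DT/aggressive fibromatosis (AF".

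**The concern.** For a subject who enters with a growing tumor, stable disease at 1 year is a change of course. For a subject who enters on symptoms with a tumor that is not growing, it may be no change at all. The pooled rate gives both the same weight. Symptoms, the reason the second group entered, are not part of the decision count.

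Two comparisons depend on this. Against the 0.5 null, a pooled rate above threshold could partly reflect who was enrolled, if the series behind the null had fewer non-growing tumors. Against nirogacestat alone, the protocol's own description puts only progressive or progressing tumors in the comparator trials, so any comparison of disease control sets a mixed population beside a progressing one. With a single checklist box for criterion 1, separating the groups later would mean going back to charts, and the investigator-discretion route makes that harder.

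**Working it through.** **1. The plan's own figures.** With X ~ Binomial(20, p), type I error is P(X ≥ c | p = 0.5) and power is P(X ≥ c | p = 0.8).

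| Cut-off c | Type I error | Power |
|---|---|---|
| 11 (section 10.4.4) | 41.2% | 99.7% |
| 14 | 5.8% | 91.3% |
| 15 | 2.1% | 80.4% |

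The smallest cut-off that holds one-sided 5% is 15. The stated 100.0% power is not reproduced at that level; only the cut-off of 11 comes close, and its type I error is 41.2%. That contradiction is a separate error. To keep it from being counted here, the effect of entry mix is judged at 15 of 20.

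**2. Inputs that the protocol does not give (assumptions).**
- n_s: number of the 20 who are symptomatic-only and not growing; taken as 5 or 10.
- q: their 1-year rate of CR, PR or SD with no drug effect; taken as 0.8 or 0.9.
- b: the same rate in progressing entrants. It is 0.5 if the null describes them; 0.4 is also shown because section 10.4.3 says recurrence is above 50%.

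**3. Formula.** The no-effect count is X = Binomial(20 − n_s, b) + Binomial(n_s, q), with mean rate [(20 − n_s)·b + n_s·q]/20. For n_s = 5, b = 0.5, q = 0.8 the mean is (7.5 + 4)/20 = 0.575.

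**4. Chance of passing 15 of 20 with no drug effect.**

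| n_s | q | Mean rate, b = 0.5 | P(X ≥ 15) | Mean rate, b = 0.4 | P(X ≥ 15) |
|---|---|---|---|---|---|
| 0 | – | 0.50 | 2.1% | 0.40 | 0.2% |
| 5 | 0.8 | 0.575 | 7.7% | 0.50 | 1.5% |
| 10 | 0.8 | 0.65 | 23% | 0.60 | 10% |
| 10 | 0.9 | 0.70 | 40% | 0.65 | 20% |

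The row with b = 0.4, n_s = 5 and q = 0.8 shows the benign case. There the mixed population has a no-effect rate of exactly 0.5, as it would if the institutional series had that same mix, and the test holds its level (1.5%).

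**5. The nirogacestat-alone comparison.** The mismatch is textual and does not depend on the origin of the null: progressing or symptomatic here, progressive or progressing there. It affects outcomes in which stable disease counts. It does not enter in the same way for objective response, which is what section 1.1 cites for nirogacestat alone (29%, and 2 of 17 at 1 year).

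**The case against.** The strongest reply is that the null may already cover these patients. Section 10.4.3 speaks of subtotally ablated desmoids without restricting them to growing ones. If the series had the same mix, inflation against 0.5 is nil. This stands, and it is why the conclusion is conditional.

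Second, parts of the text point to a low no-effect rate. Section 10.4.3 says recurrence exceeds 50%, section 1.1 says most incompletely ablated patients have clear recurrence at 6 months, and section 1.2.1 calls progression inevitable after incomplete ablation. Nor does any section give the post-ablation stability of symptomatic-only tumors, so q of 0.8 to 0.9 is unsupported. This also stands. The b = 0.4 columns show the consequence: at 15 of 20, the 5% level is exceeded with 10 such entrants but not with 5.

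Third, a reader might infer that the decision rule declares efficacy more often than not without any effect. The documents do not support that as a finding about eligibility. The cut-off of 11 alone gives 41.2% at 0.5. Passing one half then needs an assumed share and q with progressors at exactly 0.5: 5 entrants at q = 0.8 give 68% with b = 0.5 but 40% with b = 0.4.

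Fourth, a reader might infer that the comparison with nirogacestat alone is tilted towards the combination. The mismatch is real, but its effect cannot be sized. The cited benchmarks are response rates, the NCI study reported no progression among its evaluable subjects, so disease control there is already at its ceiling, and section 10 attaches no test to the comparison.

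Finally, subgroup summaries often belong in a SAP, and quality of life is assessed separately. That is fair for the tables. It does not cover recording the entry route at enrolment or stating the basis of the null, which section 10.4.3 sets out to justify.

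**Conclusion.** The concern holds in a conditional form. The text establishes that growth is not required for entry on symptoms, that unchanged disease is a success, that one pooled rate is compared with 0.5, and that the nirogacestat-alone trials enrolled progressive or progressing tumors. It does not establish the share of symptomatic-only entrants, their no-effect stability rate, or the entry mix behind the null.

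If the institutional series was mostly growing tumors, the chance of a false efficacy conclusion rises with the number of symptomatic-only entrants. At 15 of 20 the illustrative range is 7.7% to 40% with b = 0.5 and 1.5% to 20% with b = 0.4, against 2.1% and 0.2% with no such entrants. If the series had the same mix, there is no inflation against the null and only the mismatch with the nirogacestat-alone trials is left. This is a cheap improvement that limits what the trial could wrongly conclude; it does not show that the design is invalid.

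**What to change.** Leave eligibility unchanged, and:

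1. Add a checklist field to criterion 1 recording which route was met: RECIST progression in the past 12 months, or symptomatic only (including investigator discretion).
2. In section 10.2.1.2, report CBR with its exact 95% interval for RECIST progressors and for symptomatic-only entrants, beside the pooled CBR.
3. In the synopsis, restrict the disease-control comparison with nirogacestat-alone trials to RECIST progressors.
4. In section 10.4.3, state the entry mix (growing or symptomatic only) of the institutional series behind the 0.5 null.

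The cost is one data field and some wording. The downside is imprecision. At an observed 80%, the Clopper-Pearson interval is 56% to 94% for 16 of 20, 52% to 96% for 12 of 15, and 44% to 97% for 8 of 10, so the split estimates are descriptive.

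A further requirement that CBR in progressors exceed 50% is not recommended. With a cut-off of 15 it changes nothing at 5 or 8 symptomatic-only entrants, and with 10 at q = 0.9 (b = 0.5) it lowers no-effect passing only from 40% to 31%.

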
3.1.2. Exclusion Criteria

Prospective Participants Must NOT Meet ANY of These Exclusion Criteria	Yes	No	Supporting Documentation *
1. Participant previously received or is currently receiving therapy with GS inhibitors or anti-Notch antibody therapy.			
2. Participant is currently using any treatment for DT including tyrosine kinase inhibitors (TKIs), NSAIDS (chronic daily use – except as in inclusion criterion 4) or any investigational treatment 28 days (or 5 half-lives, whichever is longer) prior to the first dose of study treatment.			
3. Participant is currently using or anticipates using food or drugs that are known strong or moderate cytochrome P450 3A4 (CYP3A4) inhibitors, or strong CYP3a inducers within 14 days prior to the first dose of study treatment.			
4. Participant has known hypersensitivity to the active substance or to any of the excipients of nirogacestat.			
5. Participant with active or chronic infection at the time of informed consent and during the screening period.			
6. Participant has known malabsorption syndrome or preexisting gastrointestinal condition that may impair absorption of nirogacestat (e.g., gastric bypass, lap band, or other gastric procedures that would alter absorption); delivery of nirogacestat via nasogastric tube or gastrostomy tube is not allowed.			

Prospective Participants Must NOT Meet ANY of These Exclusion Criteria	Yes	No	Supporting Documentation *
7. History of other high-grade malignancy ≤ 2 years previous. Exceptions include prior or concurrent malignancy whose natural history or treatment does not have the potential to interfere with the safety or efficacy assessment of the investigational regimen; adequately treated basal cell or squamous cell skin cancer; or adequately treated, with curative intent, cancer from which the subject is currently in complete remission per study Principal Investigator's (PI's) judgment. Specific situations can be discussed with study PI.			
8. Participant has experienced any of the following within 6 months of signing informed consent: 
 • Clinically significant cardiac disease (New York Heart Association Class III or IV); • Myocardial infarction • Severe / unstable angina • Coronary / peripheral artery bypass graft • Symptomatic congestive heart failure • Cerebrovascular accident • Transient ischemic attack • Symptomatic pulmonary embolism 			
9. Participant has congenital long QT syndrome.			
10. Participant has a history of additional risk factors for Torsades de pointes (TdP) (e.g., heart failure, hypokalemia, family history of long QT syndrome).			
11. Participant has current or chronic history of liver disease or known hepatic or biliary abnormalities (except for Gilbert's syndrome or asymptomatic gallstones).			

Prospective Participants Must NOT Meet ANY of These Exclusion Criteria	Yes	No	Supporting Documentation *
12. Participant is currently enrolled or was enrolled within 28 days of first dose of study treatment in another clinical study with any investigational drug or device.			

* All subject files must include supporting documentation to confirm subject eligibility. The method of confirmation can include, but is not limited to, laboratory test results, radiology test results, subject self-report, and medical record review.

V. Statement of Eligibility

By signing this form of this trial I verify that this subject is:

eligible for participation in the study ineligible for participation in the study

Study Coordinator printed name:	Date:
Signature:	

Investigator printed name:	Date:
Signature:	

Triple-check reviewer printed name:	Date:
Signature:	

